14. RVSP

B. LV Measures

1. Interventricular septum (mm)
2. Posterior wall thickness
3. LVID end-diastole
4. LVID end-systole
5. ESV
6. EDV
7. LVEF

C. Mitral Valve

1. Degree of MR (Trace/none, mild, moderate, severe)
2. Mechanism of MR

D. Aortic Valve

1. Aortic stenosis (y/n)
2. Aortic Regurgitation (None, trace, mild, moderate or severe)

Appendix II: Moderate Tricuspid Regurgitation Trial Echocardiographic Image Acquisition Protocol: 3D Image Echo Protocol

General Considerations:

Optimize ECG tracing, avoid stitching artifacts.

Maximize frame rate-minimum frame rate needed 10 Hz but the higher the better.

Only Full Volume Datasets; Do not acquire in Live 3D or 3D Zoom modes

a. Focused RV Apical 4 Chamber view:

-Full volume 3D data set in modified AP4 view focused on RV and RA. This view is obtained in apical 4 chamber window with probe positioned LATERALLY and tilted ANTERIORLY to include the RVOT. If biplane or x-plane imaging is available, visualization of RVOT can be confirmed (see figure). Obtain a FV 4 beat acquisition (with breath hold), HVR mode (if available) and one beat acquisition; repeat x 1

-Full volume 3D color Doppler dataset across tricuspid valve: 4 beat acquisition with breath hold and one beat acquisition

b. Standard apical 4 chamber view: Optimize depth and sector image to obtain standard apical 4 chamber including both ventricles and atria

-Full volume 3D data set in AP4 view- 4 beat acquisition (with breath hold), HVR mode and one beat acquisition; repeat x 1

c. Full volume 3D data set of RV outflow view (parasternal window)-4 beat acquisition (with breath hold), HVR mode and one beat acquisition; repeat x 1

Appendix III: New York Heart Association Classification (NYHA)

Class	Patient Symptoms
Class I (Asymptomatic)	No limitation of physical activity. Ordinary physical activity does not cause undue fatigue, palpitation, or dyspnea (shortness of breath).
Class II (Mild)	Slight limitation of physical activity. Comfortable at rest, but ordinary physical activity results in fatigue, palpitation, or dyspnea.
Class III (Moderate)	Marked limitation of physical activity. Comfortable at rest, but less than ordinary activity causes fatigue, palpitation, or dyspnea.
Class IV (Severe)	Unable to carry out any physical activity without discomfort. Symptoms of cardiac insufficiency at rest. If any physical activity is undertaken, discomfort is increased.

Appendix IV: Six-Minute Walk Test Instructions

The walking test will be conducted in an enclosed corridor (preferably free of distractions) on a course that is 60 feet long (Guyatt, 1985³). The corridor will be divided into 5-foot sections using a method unnoticeable to the patient. Chairs will be placed at either end of the 60-foot course markers. The distance covered during the preceding walk test will not be revealed to the patient during the study.

Before the test, the patient will sit quietly for 10 minutes. These instructions will be read verbatim to the patient:

THE PURPOSE OF THIS TEST IS TO FIND OUT HOW FAR YOU CAN WALK IN SIX-MINUTES. YOU WILL START FROM THIS POINT AND FOLLOW THE HALLWAY TO THE CHAIR AT THE END, THEN TURN AROUND AND WALK BACK. WHEN YOU ARRIVE BACK AT THE STARTING POINT, YOU WILL GO BACK AND FORTH AGAIN. YOU WILL GO BACK AND FORTH AS MANY TIMES AS YOU CAN IN THE SIX-MINUTE PERIOD. IF YOU NEED TO, YOU MAY STOP AND REST. JUST REMAIN WHERE YOU ARE UNTIL YOU CAN GO ON AGAIN. HOWEVER, THE MOST IMPORTANT THING ABOUT THE TEST IS THAT YOU COVER AS MUCH GROUND AS YOU POSSIBLY CAN DURING THE SIX MINUTES. I WILL TELL YOU THE TIME, AND I WILL LET YOU KNOW WHEN THE SIX MINUTES ARE UP. WHEN I SAY STOP, PLEASE STAND RIGHT WHERE YOU ARE.

DO YOU HAVE ANY QUESTIONS ABOUT THE TEST?

PLEASE EXPLAIN TO ME WHAT YOU ARE GOING TO DO.

Repeat the entire instructions if the patient does not seem to understand.

Repeat the sentence:

THE MOST IMPORTANT THING ABOUT THE TEST IS THAT YOU COVER AS MUCH GROUND AS YOU POSSIBLY CAN DURING THE SIX MINUTES.

ARE YOU READY?

START WHEN I SAY "GO"

³ Kirshner, B, Guyatt, G. (1985) A methodological framework for assessing health indices. *Journal of Chronic Diseases* 38: 27–36.

During the test, the walking pace of the patient should not be influenced. The test supervisor must walk behind the patient - not walk with, rush up behind, or rush past the patient.

While walking, the patient will be encouraged every 30 seconds with the following phrases:

0-3 minutes:

**THAT'S IT; YOU'VE GOT THE IDEA.
YOU'RE DOING WELL.
KEEP IT UP NOW.**

3-6 minutes:

**REMEMBER, AS FAR AS YOU CAN GO.
WE'LL WANT YOU TO GO AS FAR AS YOU POSSIBLY CAN.
THAT'S IT; KEEP WORKING AT IT.
COME ON; KEEP GOING.**

The patient should be spoken to only at the 30-second encouragements and no response should be made to the patient's questions about the time and distance elapsed. If the patient is not concentrating on the walking, the patient can be reminded at a 30-second mark:

THIS IS A WALKING TEST. TALKING WILL UTILIZE YOUR ENERGY RESERVE AND INTERFERE WITH YOUR PERFORMANCE.

Encouragement phrases can be repeated as needed. For example, if the patient is slowing down and expresses that he/she wants to stop, say:

REMEMBER, IF YOU NEED TO, YOU MAY REST. JUST REMAIN WHERE YOU ARE UNTIL YOU CAN GO ON AGAIN.

If necessary, the patient may rest in a course marker chair although he/she should not be encouraged to do so.

The patient will be told the time elapsed at 2 and 4 minutes, i.e.:

**YOU HAVE COMPLETED 2 MINUTES
And
YOU HAVE COMPLETED 4 MINUTES**

At the end of the test, the patient should not move from where he/she was told to "STOP" until the distance walked (measured to the nearest foot) has been recorded.

Record the DISTANCE WALKED during the six-minute test.

Appendix V: Frailty Assessment – Gait Speed Test Instructions

The addition of the Gait Speed test to assess frailty offers a quantifiable way to capture frailty in this trial population. Other approaches to assessing frailty were reviewed, but the Gait Speed test serves as the simplest and most effective test in measuring frailty.

The assessment is an average of three 5 meter walks.

The test can be performed on any patient able to walk 5 meters using the guidelines below.

Accompany the patient to the designated area – well lit, unobstructed, and containing clearly indicated markings at 0 and 5 meters.

Position patient with feet behind, but just touching the 0 meter start line.

Instruct the patient to “walk at a comfortable pace” until a few steps past the 5 meter mark. Note, the patient should not slow down before the 5 meter mark.

Begin each trial with the word “Go.”

Start the timer at the first footfall after the 0 meter line.

Stop the timer at the first footfall after the 5 meter line.

Repeat the 5 meter walk three times, allowing for sufficient time for recuperation between trials.

Record the times, in seconds, it takes to complete each trial, on the data collection form and calculate the average speed.

Note: A patient can use a walking aid (cane, walker). For patients receiving an IV drip, that test should be performed without the IV only if it can be interrupted temporarily without any potential risk to the patient. If not, it can be performed with the patient pushing the IV pole.

AE	Adverse event
AV	Atrioventricular
CABG	Coronary artery bypass grafting
CEA	Cost-effectiveness analysis
CTSN	Cardiothoracic Surgical Trials Network
DCC	Data and Clinical Coordinating Center
DGTHG	German Society for Thoracic and Cardiovascular Surgery (Deutschen Gesellschaft für Thorax-, Herz- und Gefäßchirurgie)
DSMB	Data and Safety Monitoring Board
EAC	Event Adjudication Committee
EC	Ethics Committee
EQ-5D	EuroQoL
ICER	Incremental cost effectiveness ratio
InCHOIR	International Center for Health Outcomes & Innovation Research
IRB	Institutional Review Board
KCCQ	Kansas City Cardiomyopathy Questionnaire
LOS	Length of stay
MACCE	Major adverse cardiac and cerebrovascular event
MR	Mitral regurgitation
MV	Mitral valve
MVS	Mitral valve surgery
NHLBI	National Heart, Lung, and Blood Institute
NYHA	New York Heart Association
QALY	Quality adjusted life years
QOL	Quality of Life
REB	Research Ethics Board
RV	Right Ventricle
RVFAC	Right ventricular fractional area change
SAE	Serious adverse event
SAP	Statistical Analytical Plan
SF-12	Short Form 12
6MWT	Six Minute Walk Test
TAPSE	Tricuspid annular plane systolic excursion
TEE	Trans-esophageal echocardiography
TR	Tricuspid regurgitation
TTE	Transthoracic echocardiography
TV	Tricuspid valve

PURPOSE OF STATISTICAL ANALYTICAL PLAN (SAP)

The purpose of this SAP is to outline the planned analyses to be completed for the TR trial. The analyses identified in this SAP will be included in abstracts and manuscripts reporting the results of the trial. Exploratory analyses not necessarily identified in this SAP may also be performed. Any post hoc, or unplanned, analyses not explicitly identified in this SAP will be clearly identified as such in any published papers from this study. This SAP may be updated in response to additional developments, either within or outside the trial. All revisions will be made prior to the data lock and the primary analysis.

1. INTRODUCTION

The presence of moderate or severe TR is commonly encountered, affecting over 1.6 million people in the United States alone (Taramasso et al., 2012). As intrinsic pathology of the TV is rare, most TR is functional, defined as regurgitation in the presence of anatomically normal leaflets and chords. The precise mechanism by which functional TR develops is thought to be due to tricuspid annular dilation as well as by right ventricular (RV) enlargement and dysfunction associated with MV pathology in the presence of systolic and/or diastolic dysfunction and/or significant pulmonary hypertension (Dreyfus, Martin, Chan, Dulguerov, & Alexandrescu, 2015).

Although the clinical context in which TR occurs may influence prognosis, there are numerous reports that demonstrate the presence of TR being associated with increased mortality. Patients who do survive and develop more severe TR are more likely to develop New York Heart Association class III-IV symptoms (Groves, Lewis, Ikram, Maire, & Hall, 1991; Ruel et al., 2004) and decreased quality of life.

In 1967, Braunwald and colleagues demonstrated that correction of left-sided disease allowed for resolution of TR (Morrow, Oldham, Elkins, & Braunwald, 1967). In more recent years, however, this philosophy has been challenged by some, on account of observations that TR may in fact resolve only in a minority of cases. Overall data on the postoperative course and clinical sequelae of TR are conflicting, largely due to heterogeneous surgical management and MV pathologies.

In patients with severe TR already undergoing surgery for left valvular pathology, surgical correction is recommended by the AHA/ACC and ESC guidelines (Nishimura et al., 2014). Significant equipoise exists, however, as to the optimal approach for patients with only moderate TR or mild TR with annular dilation. Some argue that performing a TV annuloplasty at the time of MVS influences the incidence of right heart failure and improves long term survival, yet others believe the risk of an additional surgical procedure outweighs the potential benefit (Yilmaz et al., 2011).

The CTSN, therefore, designed a trial to evaluate the efficacy and safety of concomitant TR annuloplasty at the time of MVS. This document serves as the SAP for the TR trial.

2. STUDY OBJECTIVES

The overall objective of this study is to evaluate the safety and efficacy of tricuspid valve (TV) repair in the setting of mitral valve surgery (MVS) for degenerative mitral valve (MV) disease. Specifically, this study compares the surgical approach of combining TV annuloplasty with clinically indicated MVS to performing MVS alone.

2.1 Primary Objective

The primary aim of this trial is to evaluate the impact of these two surgical approaches on the composite endpoint of death and reoperation for tricuspid regurgitation (TR), or progression of TR, either by two grades from baseline (i.e. *prior* to randomization), *or* by the presence of

severe TR at 2 year follow-up.

2.2 Secondary Objectives

Secondary aims of this trial include assessment of the impact of these two surgical approaches on right heart performance and function, mortality, adverse events (AEs), quality of life (QOL), functional status, presence and severity of TR, and health resource use.

3. STUDY OVERVIEW

3.1 Study Design

This is a prospective, multi-center, randomized clinical trial in patients undergoing MVS for degenerative MV disease. Patients will be randomized (1:1) to receive either MVS + TV annuloplasty or MVS alone.

3.1.1 Study Duration and Time Points

All patients will be followed for 60 months post-randomization. Endpoints will be measured at 30 days, 6, 12, 18, and 24 months. Survival will continue to be measured after the 24-month visit via vital sign checks at 36, 48 and 60 months.

3.1.2 Randomization and Masking

Patients will be randomly assigned (1:1) to MVS + TV annuloplasty or MVS alone. Patient randomization will be stratified by TR severity and by clinical center. The randomization procedure will be performed intra-operatively, following the placement of the TEE probe and after visualization and confirmation of cardiac anatomy eligibility, in order to minimize the likelihood of enrolling patients in the study with unexpected surgical contra-indications to TV repair. Randomization will be performed centrally through a Web-based data collection system that automates the delivery of the randomization assignments. The treatment assignment will be viewed by the site coordinator electronically, in a secure fashion, and electronic verification of the treatment assignment will be required before proceeding with the treatment intervention.

Neither patients nor investigators will be blinded to treatment assignment due to the nature of the treatment intervention. Investigators will, however, be blinded to all data from other clinical sites, except serious unexpected AEs that are possibly or probably related to the investigational procedure for IRB/REB/EC reporting purposes. All echocardiograms will be analyzed by echocardiography core laboratory (Echo Core Lab) personnel who will be blinded to clinical outcomes. Adverse events (AEs) will be adjudicated by an Event Adjudication Committee (EAC) and trial oversight will be provided by an independent Data and Safety Monitoring Board (DSMB).

4. ANALYSIS POPULATIONS

Two populations will be used for all summaries and analyses.

Screened Population

The screened population will consist of all screened patients. A screened patient is defined as a consented subject who was referred to, or identified at a clinical site for consideration of entry into the study, and for whom some preliminary (i.e., medical record) data have been collected and/or reviewed.

Intent-to-Treat (ITT) Population

The ITT population will consist of all randomized subjects grouped by their assignment at randomization whether or not they actually received the treatment to which they were assigned. This sample will be used for summaries and analyses of the primary endpoint and the secondary clinical endpoints.

5. STUDY ENDPOINTS

5.1 Primary Endpoint

The primary endpoint will be a composite of death, reoperation for TR, or progression of TR from baseline, prior to randomization, by two grades or the presence of severe TR at 2 years post randomization.

Degree of TV regurgitation will be categorized according to American Society of Echocardiography guidelines as none/mild/moderate/severe. Trace regurgitation is also used in the event that regurgitation is barely detected.

5.2 Secondary Clinical Endpoints

The following secondary clinical endpoints will be assessed:

5.2.1 Clinical and Functional Outcomes

- A composite of major adverse cardiac and cerebrovascular events (MACCE), including stroke, death, and serious heart failure events by 24 months post-randomization
- Re-operation for TR by 24 months post-randomization
- NYHA classification at 30 days, 6, 12 and 24 months post-randomization.
- Diuretic Use at 30 days, 6, 12 and 24 months
- 6MWT at 30 days, 6, 12 and 24 months post-randomization.
- Gait Speed Test for Frailty at 12 and 24 months post-randomization.

5.2.2 Echocardiography

All echocardiography outcomes are measured by transthoracic 2D echocardiography unless otherwise noted

- Degree of TR at index hospital discharge
- Degree of TR at 12 and 24 months
- RV size at 12 and 24 months
- RV function (normal, mildly impaired, moderately impaired, severely impaired, peak tricuspid annular velocity, TAPSE, RVFAC) at 12 and 24 months
- Pulmonary artery pressure at 12 and 24 months
- RV volume at 12 and 24 months as measured by transthoracic 3D echocardiography

5.2.3 Quality of Life

- SF-12 at 6, 12, 18 and 24 months post-randomization.
- KCCQ at 6, 12, 18 and 24 months post-randomization.
- EQ-5D at 6, 12, 18 and 24 months post-randomization.

5.2.4 Survival

- Perioperative mortality (in-hospital or 30-day mortality)
- Mortality through 24 months post-randomization
- Mortality through 60 months post-randomization

5.2.5 Serious Adverse Events

- Frequency of SAEs
- AV-Block requiring pacemaker implantation
- New-onset atrial fibrillation

5.2.6 Hospitalizations

- Index hospitalization LOS and ICU days
- All-cause readmissions and readmissions for heart failure and TR re-operation through the first 30 days following surgery and through 24 months post-randomization

5.2.7 Economic Outcomes

- Cost
- Cost-effectiveness

6. STATISTICAL METHODOLOGY

6.1 General Principles

Study day will be calculated from the reference start date, and will be used to show the study days of assessments and events. Reference start date is defined as the date of randomization unless otherwise specified. In analyses of index length of stay, index ICU days, peri-operative (30 day) mortality, and peri-operative (30 day) readmissions the reference date is

the date of surgery. In the situation where the event date is partial or missing, study day, and any corresponding durations are to appear partial or missing in listings. If a missing event date, such as a discharge date for a hospital readmission, is necessary to calculate patient-time at risk, the missing event date will be imputed using the median length observed for similar events.

Continuous variables will be summarized using the following descriptive statistics: number of non-missing values, means, standard deviations, medians, interquartile range, maximum, and minimum. Categorical variables will be summarized using number of non-missing values, counts and percentages.

Rates of events will be calculated as the ratio of the total number of events recorded divided by the total patient-time. Total patient-time will be calculated by summing the time (in study time units, e.g., days, months or years) that patients were at risk for a specific event from the reference time point until either study exit or the end of the time period of interest. Rates and 95% confidence intervals will be reported.

Time-to-event variables will be summarized using the Kaplan-Meier method or, in the presence of competing risk, the Gray method (Gray, 1988).

For any variable measured at multiple points in time, change from baseline will be calculated as the difference between the value of the variable at a specific point in time (e.g. 1 year) minus the baseline value. Relative change from baseline will be calculated as the value of a parameter at a specific point in time minus the baseline value of the parameter divided by the baseline value of the parameter. Percent change will be calculated as the relative change multiplied by 100.

All hypothesis testing will be conducted at the 0.05 two-sided significance level unless otherwise specified. P-values will be rounded to three decimal places. P-values less than 0.001 will be reported as <0.001 in tables. P-values greater than 0.999 will be reported as >0.999.

Should any of the statistical methods proposed prove unsuitable during data analysis, more appropriate methods will be used. These include data transformation (for example to a logarithmic scale) to satisfy model assumptions such as normally distributed residuals with constant variance, the application of non-parametric techniques or the use of a different link function or modeling technique.

Additional ad-hoc analyses may be conducted as deemed appropriate.

All analyses will be conducted using SAS V9.4 or higher.

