6.5.2 Analyses of Secondary Clinical Endpoints

6.5.2.1 Clinical and Functional Outcomes

MACCE: The rate of major cerebrovascular or cardiac events (defined as the

composite event of death, stroke, and serious heart failure events) will be compared between randomization groups over 24 months post-randomization using a Cox proportional hazards regression model.

Reoperation for TR: The difference in the rate of requiring subsequent TV annuloplasty after the initial MVS will be compared between randomization groups over 24 months post-randomization. Reoperation for TR may not occur because death from any cause precedes the event; thus, it is possible that censoring patients at all-cause mortality will lead to biased estimates when analyzing time to first event. Therefore, competing risks analysis using the methods of Fine and Gray (Fine & Gray, 1999) will be used to estimate group differences.

NYHA: The distribution of NYHA at 30 days, 6, 12 and 24 months will be presented for each randomization arm and compared using chi-squared tests.

Diuretic Use: The distribution of diuretic use at 30 days, 6, 12 and 24 months will be presented for each randomization arm and compared using chi-squared tests.

Six Minute Walk: Differences between groups in the distances travelled during the 6MWT at 30 days, 6, 12 and 24 months will be compared using Wilcoxon Rank-Sum tests.

Gait Speed Tests: Differences between groups in gait speed at 12 and 24 months will be compared using Wilcoxon Rank-Sum tests.

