6.5.2.2 Echocardiography

Degree of TR: The distribution of the degree of TR at hospital discharge, 12, and 24 months will be presented for each randomization arm and compared using chi-squared tests. Between group differences in TR progression defined as presence of severe TR at 24 months, or for patients enrolled with less than moderate TR, progression by two grades compared to baseline will be compared using a two-tailed 0.05 level chi-squared test.

Additional echo parameters: RV size, RV function (normal, mildly impaired, moderately impaired, severely impaired, peak tricuspid annular velocity, TAPSE, RVFAC), and pulmonary artery pressure at 12 and 24 months will be compared between groups. RV volume as assessed by 3D TTE at 12 and 24 months will be compared between groups. Continuous variables will be compared for between group differences using the Wilcoxon Rank Sum test, and the level of function by chi-square test.

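### SAP 6.1 puts at least 54 secondary comparisons at two-sided 0.05, with no hierarchy, multiplicity control or nominal-only label

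*SAP*

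**What the plan says.** The general rule is in SAP 6.1: "All hypothesis testing will be conducted at the 0.05 two-sided significance level unless otherwise specified". SAP 6.5.2 then prescribes the secondary comparisons and sets no other level. The only level it names, for TR progression in 6.5.2.2, is again 0.05 two-tailed. The protocol's Degree of TR paragraph (Analytical Plan, Analyses of Secondary Endpoints) does the same.

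Many endpoints are compared at several visits:

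- NYHA: "The distribution of NYHA at 30 days, 6, 12 and 24 months will be presented for each randomization arm", with chi-squared tests.
- Diuretics: "The distribution of diuretic use at 30 days, 6, 12 and 24 months will be presented for each randomization arm", also with chi-squared tests.
- Walking distance: "6MWT at 30 days, 6, 12 and 24 months will be compared using Wilcoxon Rank-Sum tests".
- Frailty: "gait speed at 12 and 24 months will be compared using Wilcoxon Rank-Sum tests".
- Degree of TR: "The distribution of the degree of TR at hospital discharge, 12, and 24 months will be presented", with chi-squared tests.

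The SAP's statement of purpose adds: "The analyses identified in this SAP will be included in abstracts and manuscripts reporting the results of the trial". It requires a label in publications only for post hoc or unplanned analyses.

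Neither document contains a ranking of secondary endpoints or visits, a gatekeeping order, a split of alpha, a multiplicity adjustment, or a statement that secondary p-values are nominal.

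**The concern.** A default significance level attached to dozens of comparisons is a decision rule, and here nothing limits how often it will be met by chance. A listed secondary test that falls below 0.05 would be published as a prespecified result, with no caveat required by the plan.

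This matters more here than in many trials. The protocol expects the primary endpoint to be determined mainly by echocardiography, and it gives a clinical secondary endpoint (MACCE) a supporting role in interpretation. Patients and investigators are not blinded, so NYHA class, walking distance and quality of life are also open to expectation effects. A chance result on one of these, at one of several visits, could be given more weight than it can bear.

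**Working it through.** **1. The plan's own error control.** The documents give no family-wise figure for secondary endpoints. They do give critical values for the primary endpoint: 2.963 at the interim and 1.969 at the final analysis, with the interim at half the information. The overall two-sided alpha is 1 − P(|Z1| < 2.963 and |Z2| < 1.969), where the correlation is √0.5 = 0.707. This gives 0.0500. The primary test is therefore controlled at its stated level.

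**2. Count of secondary tests in SAP 6.5.2.**

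| Group | Tests |
|---|---|
| MACCE 1, reoperation for TR 1, NYHA 4, diuretics 4, 6MWT 4, gait speed 2 | 16 |
| Degree of TR 3, TR progression 1; RV size, RV function grade, peak annular velocity, TAPSE, RVFAC, PA pressure and RV volume at 2 visits each (14) | 18 |
| KCCQ, SF-12, EQ-5D, one test each | 3 |
| Perioperative, 24-month and 60-month mortality | 3 |
| AV block, new atrial fibrillation | 2 |
| LOS and ICU days, each in 2 regions | 4 |
| Readmission: 4 outcomes by 30 days, 3 by two years | 7 |
| Cost | 1 |
| **Total** | **54** |

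Counting both quality-of-life approaches gives 57. Individual SAE types are also tested (SAP 6.5.2.5), but their number is not stated; 0 to 15 is assumed here. Cost-effectiveness has probability intervals and no test, so it is left out.

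**3. Expected false positives if every null is true.** This is k × 0.05 and does not depend on correlation:

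- 54 × 0.05 = 2.7
- 57 × 0.05 = 2.85
- (54 + 15) × 0.05 = 3.45

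**4. Chance of at least one, if independent.** This is 1 − 0.95^k:

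- k = 54: 0.937
- k = 57: 0.946
- k = 69: 0.971
- k = 28 (one test for each of the 28 endpoints or outcome groups): 0.762

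**5. Chance of at least one, if correlated.** The documents give no correlations, so these are assumptions. Test statistics were simulated as correlated standard normals, all nulls true, 100,000 draws, counting any |Z| > 1.96 among 54.

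| Assumed correlation | P(at least one) |
|---|---|
| 0.5 within endpoint, 0 between | 0.92 |
| 0.7 within, 0.2 between | 0.85 |
| 0.8 within, 0.3 between | 0.77 |
| 0.3 common to all | 0.82 |
| 0.5 common to all | 0.64 |
| 0.7 common to all | 0.42 |

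A common correlation of 0.8 would give 0.31. That is hard to credit across outcomes as different as cost, gait speed and pacemaker implantation.

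**6. If some effects are real.** Suppose the four tests on degree of TR and TR progression are not nulls. Then 50 remain: 50 × 0.05 = 2.5 expected, and 1 − 0.95^50 = 0.923 if independent.

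**The case against.** The case against has several parts, and most of it stands.

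- **Dependence.** A reader might infer that at least one false-positive secondary finding is close to certain. The documents do not support that. The 0.94 is the ceiling for 54 independent, all-null tests. Strong dependence is built in: the same patients are measured at up to four visits, 60-month mortality contains 24-month mortality, and TR progression at 24 months is derived from the degree of TR.
- **All nulls true.** This is least plausible for degree of TR, which annuloplasty is meant to change.
- **The count.** Adding all 16 adverse event categories defined in the protocol to 57 would give 73. That double-counts, because AV block and new atrial fibrillation are already included and are defined within cardiac arrhythmias. It also counts the catch-all category.
- **Confirmatory status.** A reader might infer that the confirmatory result cannot be told apart from the rest. It can. Only the primary endpoint has a formal null hypothesis (SAP 6.5.1), a sample-size basis (6.5.1.1) and stopping boundaries (6.6).
- **No declared claim.** Nowhere do the documents say that a secondary p < 0.05 will be claimed as efficacy. The protocol describes the additional secondary analyses as supporting the primary one, and says a significant MACCE difference is not expected.
- **Publication.** Reporting every planned analysis guards against selective reporting, because readers see how many comparisons were made.

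These points limit the size of the problem but do not remove it. The supporting role is described in the protocol; the SAP, which governs reporting, omits it and sets a significance rule instead. The protocol also says that a MACCE difference in the same direction as the primary result would help validate the trial, so secondary results carry weight. Full publication shows the number of tests but does not tell a reader how to take an isolated p < 0.05.

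**Conclusion.** The point holds as a gap in the reporting rule. It does not threaten the primary analysis. The plan applies two-sided 0.05 to nearly every secondary comparison, at least 54 of them, with no hierarchy, adjustment or nominal-only label.

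If all nulls were true, about 2.7 false positives are expected. The chance of at least one is 0.94 if the 54 tests are independent, up to 0.97 with an assumed 15 SAE types added, and roughly 0.4 to 0.9 under the assumed positive correlations (common correlation up to 0.7). It falls if some effects are real. The expected count rests on the tally and the all-null premise alone; the probabilities also depend on correlations that the documents do not give. The change is worth making because it is cheap and limits what can be claimed.

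**What to change.** In SAP 6.1, restrict the 0.05 decision rule to the primary endpoint, at its group-sequential critical values from SAP 6.6 where the interim look is taken. State there that:

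- secondary endpoints are reported as effect estimates with 95% CIs not adjusted for multiplicity;
- any p-values are nominal, and no significance claims are made from them;
- 24 months is the reference visit for endpoints measured repeatedly.

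Matching edits are needed, or the SAP will contradict itself:

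- Remove the separate 0.05 level for TR progression in SAP 6.5.2.2 and in the protocol's Degree of TR paragraph.
- Name an effect estimate for each chi-squared and Wilcoxon comparison. SAP 6.1 and 6.5.2.5 already plan 95% CIs for rates and for adverse event rate ratios.

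A gated confirmatory test of MACCE is not recommended, since the protocol says the trial is not powered for a MACCE difference.

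The cost is SAP wording, which the SAP allows to be revised before data lock, and one protocol sentence. No new data or patients are needed. The downside is that isolated nominally significant secondary results can no longer be claimed.
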